## Version Control

Name	Date	Version	Description
Acumen, LLC	January 24, 2023	0.1	Drafting
Acumen, LLC	February 7, 2023	0.2	Addition of a possible influenza vaccine analysis, refinement of study objectives, updated outcome definitions to include adjustments and exclusions, adjusted the prior COVID-19 definition
Acumen, LLC	February 9, 2023	0.3	Cleaned up language, restricted NH population to long term care residents only
Acumen, LLC	February 13, 2023	0.4	Moved NH analysis to follow-up, edited study population exclusions, elaborated on analysis purposes, reformatted
Acumen, LLC	February 22, 2023	0.5	Removed prior COVID-19 subgroup and clarified exclusion/censoring criteria. Made 508 compliance edits.

## List of Abbreviations

AESI	Adverse event of special interest
AR	Attributable risk
CDC	Centers for Disease Control and Prevention
CMS	Centers for Medicare & Medicaid Services
CPT	Current Procedural Terminology
EUA	Emergency Use Authorization
FDA	Food and Drug Administration
FFS	Fee for Service
HCPCS	Healthcare Common Procedure Coding System
HS	Hemorrhagic stroke
IP	Inpatient
IRR	Incidence rate ratio
MDS	Minimum Data Set
NRS	Near real-time surveillance
NHC	Nursing Home Compare
NHS	Non-hemorrhagic stroke
NHS/TIA	Non-hemorrhagic stroke or transient ischemic attack
OBPV	Office of Biostatistics and Pharmacovigilance
OP-ED	Outpatient emergency department
OP/PB	Outpatient or Professional
POS	Place of Service
PPV	Positive predictive value
RCA	Rapid cycle analysis
SCCS	Self-controlled case series
SE	Standard error

SSD Shared Systems Data  
TIA Transient ischemic attack  
VSD Vaccine Safety Datalink

# 1 Background

On August 31, 2022 the U.S. Food and Drug Administration (FDA) authorized bivalent formulations of both the Moderna and Pfizer COVID-19 vaccines for use as a booster through emergency use authorization (EUA). The Pfizer-BioNTech COVID-19 Vaccine, Bivalent (BNT162b2 Bivalent (WT/OMI BA.4/BA.5) and Moderna COVID-19 Vaccine, Bivalent (mRNA-1273.222) boosters include an mRNA component of the original COVID-19 strain as well as an mRNA component from the BA.4 and BA.5 Omicron variants. Pfizer-BioNTech COVID-19 Vaccine, Bivalent is currently recommended for those 5 years of age and older, and the Moderna COVID-19 Vaccine, Bivalent is currently recommended for those 6 months of age and older.

On January 13, 2023 the U.S. FDA and the Centers for Disease Control and Prevention (CDC) issued a public communication concerning the identification of a preliminary safety signal for ischemic stroke among persons aged 65 years who received the Pfizer-BioNTech COVID-19 Vaccine, Bivalent in the CDC's Vaccine Safety Datalink (VSD) near real-time surveillance (NRS) system. The risk of stroke was identified in the 1-21 days following vaccination compared to 22-44 days following vaccination. As the communication indicates: "Following the availability and use of the updated (bivalent) COVID-19 vaccines, CDC's Vaccine Safety Datalink (VSD), a near real-time surveillance system, met the statistical criteria to prompt additional investigation into whether there was a safety concern for ischemic stroke in elderly persons who received the Pfizer-BioNTech COVID-19 Vaccine, Bivalent. Rapid-response investigation of the signal in the VSD raised a question of whether people 65 and older who have received the Pfizer-BioNTech COVID-19 Vaccine, Bivalent were more likely to have an ischemic stroke in the 21 days following vaccination compared with days 22-44 following vaccination." The signal was not identified with Moderna COVID-19 Vaccine, Bivalent. No other safety surveillance systems, notably FDA's Medicare Near Real-Time Surveillance, have identified a risk of stroke following the bivalent boosters among any age group.

On January 26, 2023 CDC presented these findings at a Vaccines and Related Biologic Products Advisory Committee meeting. At this meeting CDC noted that the risk of stroke in the population who had received a concomitant vaccination (receiving both a Pfizer-BioNTech COVID-19 Vaccine, Bivalent and a high-dose or adjuvanted influenza vaccines on the same day) was higher than the risk of stroke following receipt of the Pfizer-BioNTech COVID-19 Vaccine, Bivalent alone.

The NRS methods used by FDA and CDC have limitations and produce only a crude measure of association between an exposure and an outcome. A statistically significant result in these systems should be cautiously interpreted as it does not necessarily indicate an increased risk of adverse events of special interest (AESI) in the vaccinated population. Although the NRS systems adjusted for factors such as nursing home residency status, age, sex, and race, they did not adjust for any other potential confounding. In depth analyses which adjust for confounding are necessary to evaluate the signal.

The CBER Surveillance program has developed this protocol for use in conducting a more rigorous follow-up study of the results on the stroke outcomes identified in CDC VSD to determine whether there is an elevated risk using a more fully-controlled study design. This study will use a self-controlled case

series (SCCS) analysis to evaluate the preliminary stroke signal and the potential association between Pfizer-BioNTech COVID-19 Vaccine, Bivalent and stroke, including non-hemorrhagic stroke, hemorrhagic stroke, and transient ischemic attacks. The study will evaluate the Moderna COVID-19 Vaccine, Bivalent using the same methods. The study will also evaluate the risk of stroke outcomes following concomitant vaccination with a high-dose or adjuvanted influenza vaccine during the same study period. If a higher risk is identified post concomitant vaccination, this study will additionally evaluate the independent risk of stroke outcomes following high-dose or adjuvanted influenza vaccination.

## 2 Study Objectives

The objective of this study is to use a SCCS analysis to evaluate the risk of stroke outcomes after exposure to the Pfizer-BioNTech COVID-19 Vaccine, Bivalent and Moderna COVID-19 Vaccine, Bivalent booster doses (bivalent boosters) among Medicare beneficiaries age 65 years and older who do not reside in a nursing home facility.

### 2.1 Primary Objectives

The primary objectives of this study are to evaluate:

- I. The risk of stroke outcomes (as defined in Section 4.3) following exposure to the Pfizer-BioNTech COVID-19 Vaccine, Bivalent and Moderna COVID-19 Vaccine, Bivalent booster doses (by brand) among Medicare beneficiaries age 65+.
- II. The risk of stroke outcomes following exposure to the Pfizer-BioNTech COVID-19 Vaccine, Bivalent and Moderna COVID-19 Vaccine, Bivalent booster doses (by brand) among age groups, those with a prior COVID-19 infection, and those who received a concomitant (same day administration) high-dose or adjuvanted influenza vaccine (see Section 5.5.3 for subgroup definitions).

The analysis for the primary objectives compares the risk of each outcome in a time interval after vaccination (risk window) to that in time intervals post-vaccination after completion of the risk window (control window) within the observation period.

### 2.2 Secondary Objectives

The secondary objectives of this study are to:

- I. Conduct a temporal scan to identify clusters of stroke outcomes after exposure to the Pfizer-BioNTech COVID-19 Vaccine, Bivalent and Moderna COVID-19 Vaccine, Bivalent COVID-19 mRNA bivalent booster doses (by brand) among Medicare beneficiaries age 65+.
- II. Evaluate the independent risk of stroke outcomes (as defined in Section 4.3) following exposure to a high-dose or adjuvanted influenza vaccine (without concomitant administration of a bivalent booster) among Medicare beneficiaries age 65+, if power allows. This analysis will only be conducted on outcomes for which an increased risk of any stroke outcome following concomitant bivalent booster and influenza vaccination is identified.

SCCS analyses can be sensitive to the specification of intervals (risk and control). The temporal scan analysis will identify clusters of stroke outcomes for further consideration and evaluation. We will use the temporal scan analysis to validate our risk interval choices during the observation period.

## 2.3 Follow-Up Analysis

We have specified two follow-up analyses to occur at a later point in time. The objectives of these analyses are to evaluate:

- I. The risk of stroke outcomes (as defined in Section 4.3) following exposure to the Pfizer-BioNTech COVID-19 Vaccine, Bivalent and Moderna COVID-19 Vaccine, Bivalent booster doses among Medicare long-term stay nursing home residents age 65+.
- II. The risk of hemorrhagic stroke (HS), non-hemorrhagic stroke (NHS), and the combined outcome of non-hemorrhagic stroke or transient ischemic attacks (NHS/TIA) following exposure to the Pfizer-BioNTech COVID-19 Vaccine, Bivalent and Moderna COVID-19 Vaccine, Bivalent booster doses (by brand) among Medicare beneficiaries 65+ using an alternate definition of care setting (including the outpatient emergency department (OP-ED) setting in addition to the originally specified inpatient (IP) setting (see Section 4.3 for primary setting definitions).

## 3 Data Sources

The data source for this study is the US Medicare claims and enrollment databases in the Centers for Medicare & Medicaid Services (CMS) Shared Systems Data (SSD), for elderly persons aged 65 years and older in the US, with continuous Medicare Fee-for-Service (FFS) coverage only. Demographics and information on death is derived from the enrollment databases. Information on vaccinations, health covariates, preventive services, and outcomes are derived from Medicare Part A (inpatient) and Part B (outpatient settings and providers). Medicare claims data undergo three stages of processing: enumeration, adjudication, and final payment. CMS Medicare SSD, which consists of claims sourced after enumeration, will be used in this study. SSD is updated daily and is over 80% complete within 30-70 days depending on the care setting and outcome. Information on nursing home residency status is derived from clinical assessment of residents in the Minimum Data Set (MDS). Additionally, we will capture nursing home characteristics through the Nursing Home Compare (NHC) dataset and COVID-19 Nursing Home COVID-19 public file reported to the CDC and provided by CMS. For each person in the study, administrative claims from all care settings will be linked to create a longitudinal record of their health encounters, diagnoses, and drug prescriptions.

## 4 Exposure and Outcomes

### 4.1 Care Settings

Exposures and stroke outcomes will be identified within relevant care settings of interest, as specified based on clinical guidance. Table 1 defines the inpatient (IP), outpatient and professional (OP/PB), and outpatient emergency department (OP-ED) settings used in this study.

**Table 1. Care setting definitions**

Care Setting	Definition
Inpatient (IP)	Inpatient acute facility claims (e.g., UB-04 with type of bill = 11x)

Care Setting	Definition
Outpatient Emergency Department (OP-ED)	Outpatient facility claims (e.g., UB-04) in ED
Outpatient or Professional (OP/PB)	Outpatient facility claims UB-04) -OR- Professional claims (CMS-1500) that contain at least one non-lab place of service 

 Including all sources of professional claims (e.g., urgent care etc.)

 Independent laboratory place of service code = 81

The IP setting represents hospital inpatient acute facility claims. Hospital inpatient facility claims provide information on the care and services received by patients during the entire duration of inpatient care. These tend to have more accurate diagnosis coding compared to professional claims, given that provider facilities are reimbursed based on the types of diagnosis coded, which reflect the level of treatment required. Facilities are also generally more responsive to medical record requests initiated.

The OP/PB setting represents all outpatient and professional services claims with non-laboratory places of service, and captures the broad spectrum of outpatient care regardless of care setting or provider type. Claims with laboratory places of service are excluded, given that these claims often include “rule-out-diagnoses” that may not reflect true existing or underlying conditions present in patients. The OP-ED setting is a subset of the OP/PB setting and represents outpatient facility claims with services specifically provided in the Emergency Department (OP-ED), identified through place of service (POS) and revenue (REV) codes, in PB and OP settings, respectively.

## 4.2 Exposures

Exposures for the primary analysis are defined as the receipt of any bivalent booster dose, as identified by Current Procedural Terminology (CPT®)/Healthcare Common Procedure Coding System (HCPCS) codes in any care setting (Table 2).

**Table 2. Healthcare Common Procedure Coding System (HCPCS)/ Current Procedural Terminology (CPT) for COVID-19 Bivalent Booster Doses as of February 23, 2023**

HCPCS/CPT Code	Manufacturer	Name	Vaccine Administration Code	Age Group
91312	Pfizer-BioNTech	BNT162b2 Bivalent (WT/OMI BA.4/BA.5)	0124A	12+ years
91313	Moderna	Moderna COVID-19 Vaccine, Bivalent	0134A	18+ years

Exposures for secondary analysis II - influenza vaccines will be receipt of any high dose or adjuvanted flu vaccines, as identified by Current Procedural Terminology (CPT®)/Healthcare Common Procedure Coding System (HCPCS) codes in any care setting (Table 3).

**Table 3. Healthcare Common Procedure Coding System (HCPCS)/ Current Procedural Terminology (CPT) for High Dose/Adjuvanted Influenza Vaccines as of February 23, 2023**

HCPCS/CPT Code	Manufacturer	Name	Age Group
90662	Sanofi Pasteur	Fluzone High-Dose Quadrivalent (2022/2023)	65+ years
90694	Seqirus	Fluad Quadrivalent (Adjuvanted) (2022/2023)	65+ years

The list of valid codes will be reviewed periodically and updated if new codes are added. Patients with a claim containing a relevant code will be classified as vaccinated. In the CMS Medicare claims data, COVID-19 vaccination has been primarily billed through Part B using CPT/HCPCS codes.

If an individual has more than one vaccination code for the same brand occurring on the same day, the codes will be de-duplicated so that the individual contributes only one exposure for that brand to the study. If multiple brands are observed on the same day or multiple vaccinations (same/different brand) are observed within 3 days of each other, the given person will be excluded from the study (see Section 5.3). Prior COVID-19 vaccination is not required for inclusion in the analysis.

### 4.3 Outcomes

The stroke outcomes included in the study are hemorrhagic stroke (HS), non-hemorrhagic/ischemic stroke (NHS), transient ischemic attack (TIA), and a combined outcome which includes persons who have been diagnosed with non-hemorrhagic stroke and/or TIA (NHS/TIA). Risk following bivalent booster vaccination will be assessed separately for each of these stroke outcomes by vaccine brand. Stroke outcomes will be identified with International Classification of Diseases, Tenth Revision, Clinical Modification (ICD-10-CM) codes in either primary or secondary diagnosis positions.

The ICD-10 codes used to identify each stroke outcome, the care settings in which each outcome will be evaluated, as well as the clean and risk windows for each are described in Table 4. The first qualifying occurrence of the outcome in the observation period is defined as an incident stroke outcome only if no outcome of the same type was recorded during the preceding pre-defined clean window. The clean window is defined as a period prior to vaccination in which beneficiaries with an occurrence of an event during the pre-specified window are excluded because outcomes captured post-vaccination may be attributed to previous rather than incident risk. The risk window is defined as an interval post-vaccination during which occurrence of the stroke outcomes may be associated with the vaccine exposure and thus considered a qualifying outcome. Both clean and risk windows are selected based on literature review, consultation with subject matter experts, and to align with CDC definitions. Risk windows are further detailed in Section 5.4.2.

**Table 4. Stroke outcomes and their respective care settings, clean and risk windows**

Stroke outcomes	ICD-10 Codes	Care Setting (Primary and Secondary Analysis)	Clean Window	Risk Window
Hemorrhagic stroke (HS)	I61*, I62*	IP	365 days	1-21 days; 22-42 days
Non-hemorrhagic stroke (NHS)	I63*	IP	365 days	1-21 days; 22-42 days
Transient ischemic attack (TIA)	G45.8, G45.9	IP; OP-ED	365 days	1-21 days; 22-42 days
Non-hemorrhagic stroke or transient ischemic attack (NHS/TIA)	I63*, G45.8, G45.9	IP (NHS & TIA); OP-ED (TIA)	365 days	1-21 days; 22-42 days

Definitions: Clean Window is defined as an interval relative to stroke outcomes date used to define incident stroke outcomes where an individual enters the study cohort only if the stroke outcomes of interest did not occur during that interval. Risk Window is defined as an interval relative to exposure date during which occurrence of the stroke outcomes of interest will be included in the analyses

Follow-Up Analysis II – Care Settings will include the OP-ED setting for all outcomes.

If certain related outcome codes are observed in the one day prior to the stroke outcome of interest, we will adjust the onset date of the stroke outcome to start at the date of the related outcome. If certain outcome codes which may be associated with the onset of the stroke outcome are observed prior to or on the day of the stroke outcome, these cases will be excluded. These exclusions are implemented to clean the outcome cohort by eliminating stroke cases which are likely caused by factors other than vaccination. These exclusions are implemented in the CDC VSD Rapid Cycle Analysis (RCA). The Appendix details these adjustments/exclusions (See Appendix Table A).

## 5 Methods

### 5.1 Study Design

The SCCS design compares the incidence of adverse outcomes during periods of hypothesized excess risk due to the exposure (risk interval) to that of the control interval. Only cases (i.e., individuals with an incident stroke outcome) occurring during the study observation period contribute to risk estimation in an SCCS design, with estimation occurring within, rather than between, individuals. However, the SCCS design has a number of assumptions that have to be met in order to ensure valid unbiased risk estimates. These assumptions are outlined below:

- I. Occurrence of an outcome does not substantially affect subsequent exposures
- II. Occurrence of an outcome does not affect the observation length
- III. Outcome rates are constant within risk intervals
  - a. Outcomes must be independently recurrent or rare
  - b. The SCCS method is typically considered valid when the risk of occurrence is 10% or less

Given the fatal nature of some of the stroke outcomes included in the study (discussed below), the occurrence of an outcome can affect both subsequent exposures and reduce the observation length, thus violating both the first and the second assumptions referenced above.

A violation of the first assumption could bias the relative incidence in either direction, thus causing reverse causation bias that would affect subsequent exposures. To address this concern, the primary

analysis will be restricted to a post vaccination control interval which will avoid a bias of reverse causation but require additional data accrual after the post-vaccination risk window.

Given concerns that stroke may have a high mortality rate, we calculated the 30-day Case Fatality Rate (CFR) for each outcome by utilizing SSD data from October 31, 2021-October 31, 2022 for beneficiaries 65 years and older with a 365-day prior clean window relative to the stroke outcomes and Medicare A/B enrollment from 365 days prior to vaccination date. Table 5 displays the case fatality rates within the 30-day observation period after the outcomes.

**Table 5. 30 Day Case Fatality Rate by Outcome**

Stroke outcomes	Hemorrhagic stroke (HS)	Non-hemorrhagic stroke (NHS)	Transient ischemic attack (TIA)
Case Fatality Rate	34.3%	17.0%	2.1%

The combined NHS/TIA outcome is expected to have a similar CFR to the NHS only outcome.

Given the high mortality rate, the observation time for these beneficiaries is truncated due to death which would violate the assumption that “occurrence of the outcome doesn’t affect the observation length.” To mitigate the violation of the second assumption that the observation time is independent of the outcome (e.g. death post-stroke outcomes censors follow-up time), a modified SCCS analysis will be conducted that will utilize a “Farrington adjustment” to adjust for censored, perturbed, or curtailed post-outcome exposures.

## 5.2 Study Period

The study period will start on the date of the emergency use authorization for bivalent boosters in the U.S. (August 31, 2022) and will end on the date through which complete claims data (defined as at least 90% complete) and adequate power to assess risk estimation are available for the data source at the time of study initiation.

The completeness threshold was selected to balance the potential bias due to partially accrued observation of post-vaccination control intervals versus risk intervals, and a reasonable delay of the analysis. The 90% completeness is likely to overestimate relative risk by 10% or less. Assuming that outcome observation delays are accurately estimated from historical data, a 90% completeness threshold limits the difference in observation of outcomes in risk intervals (at most 100% complete) versus control intervals (at minimum 90% complete). If the true RR is 1, the maximum bias due to observation delay is  $(100\%/90\%)-1=11\%$ . However, in practice risk and control interval completeness will fall between 100% and 90% and we expect the potential bias due to claims delay to be smaller.

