## 5.6 Statistical Power and Sample Size Calculations

To ensure sufficient sample size, a power analysis will be conducted to evaluate the minimum detectable IRR for each of the stroke outcomes following COVID-19 bivalent booster vaccination, at 80% power and a two-sided alpha of 0.05. A minimum detectable IRR will be calculated at various data cutoff dates for the study, and the study cutoff data date will be determined based on an assessment of minimum risk detection at varied timeframes. A 90% threshold for data completeness is required at the specified data cutoff date to reduce differences in data accrual and the likelihood of observing events during risk relative to control intervals. Minimum detectable IRRs will be benchmarked against a comparable stroke outcomes risk estimate following either COVID-19 bivalent booster or third/monovalent booster doses present in the literature, to ensure sufficient sample size to detect the hypothesized IRR.

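### The 90% completeness rule leaves a one-directional upward claims-delay bias in the IRR that no planned analysis addresses; a completeness-weighted offset is a cheap addition

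*Protocol*

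**What the plan says.** Section 5.2 of the protocol ends the study period at the date up to which the data source has "complete claims data (defined as at least 90% complete" and power is adequate. It presents the threshold as a compromise between bias and postponing the analysis. On the expected consequence it says: "The 90% completeness is likely to overestimate relative risk by 10% or less". On the limit, it compares "risk intervals (at most 100% complete) versus control intervals (at minimum 90% complete" and writes "If the true RR is 1, the maximum bias due to observation delay is" (100%/90%) − 1 = 11%. It then adds that "we expect the potential bias due to claims delay to be smaller". The argument assumes that reporting delays can be estimated accurately from past data.

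Section 5.6 repeats the rule: "A 90% threshold for data completeness is required at the specified data cutoff date to reduce differences in data accrual".

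Sections 5.4.2 and 5.4.3 set the risk windows at days 1-21 and 22-42 and make the remaining follow-up, to day 90 at most, the control window. Section 5.5.2.1 writes out the conditional Poisson model with log(t) as its only offset and tests each IRR at two-sided p ≤ 0.05. Section 5.5.4 lists two sensitivity analyses: seasonality and positive predictive value.

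**The concern.** The primary analysis uses only post-vaccination control time. In every person the control days come after the risk days, so at any data cut their claims are at most as complete as those of the risk days. Missing recent claims therefore remove events mainly from the control window and push the IRR up, never down. Section 5.2 recognises this direction.

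The study follows up a signal of increased stroke risk, so the error runs towards confirming it. More cases narrow the confidence interval without shrinking the bias. In a national Medicare population, a bias of a few percent could make an IRR just above 1 statistically significant.

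Nothing planned in the protocol would reveal this. The seasonality offset uses baseline rates from earlier calendar years and does not represent unreported recent claims. The predictive-value adjustment deals with false cases, not cases that have yet to appear.

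**Working it through.** **1. The protocol's own figure.** Inputs from Section 5.2: risk completeness 100%, control completeness 90%.

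Bias = c_risk / c_control − 1 = 1.00/0.90 − 1 = 0.111, which agrees with the printed 11%. The bias is multiplicative, so the relative bound is 11.1% at any true RR, not only at 1. The 10% in the earlier sentence equals 1 − 0.90, the shortfall in the control count. A worst case of 10% would need a threshold of 1/1.10 = 90.9%, or risk completeness of 99% (0.99/0.90 − 1 = 10.0%).

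**2. Net bias, illustrative.** The 11% needs all risk days fully reported and all control days at exactly 90%. To see what is typical, I solved the expected conditional Poisson score with a true IRR of 1.

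- From the protocol: windows 1-21, 22-42 and 43-90; 90% completeness at study end; over 80% accrual within 30 to 70 days (Section 3).
- Assumed: completeness d days before study end = 1 − 0.1·exp(−kd), with k = −ln(0.2)/30 or −ln(0.2)/70; uptake either uniform or peaked around day 40; study end 60 to 180 days after 31 August 2022. The Farrington adjustment is ignored.

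Ranges over the two uptake shapes and two values of k:

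| Study end (days after 31 Aug 2022) | Bias, days 1-21 | Bias, days 22-42 |
|---|---|---|
| 60 | 5.7-7.6% | 2.8-4.5% |
| 90 | 5.3-5.8% | 3.2-3.9% |
| 120 | 3.6-4.6% | 2.6-3.1% |
| 150 | 1.8-3.5% | 1.6-2.4% |
| 180 | 0.6-2.8% | 0.5-1.9% |

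The bias was upward in every scenario and always below 10%.

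**3. Effect on the test.** Days 1-21 against days 43-90, true IRR 1, full 90-day follow-up, N cases in total (assumed):

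SE(log IRR) = √[1/(21N/90) + 1/(48N/90)]

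Rejection probability = P(|Z + ln(1+b)/SE| > 1.96), where b is the net bias.

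- N = 5,000: expected counts 1,167 and 2,667, SE = 0.0351.
  - b = 3%: shift 0.0296/0.0351 = 0.84, rejection 13.4%.
  - b = 5%: shift 0.0488/0.0351 = 1.39, rejection 28.5%.
  - b = 0.6%: shift 0.0060/0.0351 = 0.17, rejection 5.3%.
- N = 2,000: SE = 0.0555; b = 3% gives 8.3%.
- N = 1,000: SE = 0.0785; b = 3% gives 6.6%.

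**4. Effect of a completeness offset.** If the expected count in an interval is proportional to the sum of completeness over its days, using that sum in place of t brings the expected delay bias to zero, provided the completeness curve is right.

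**The case against.** The strongest reply is that the protocol hides nothing. It names the direction of the bias, gives the correct maximum, says the real figure should be smaller, and justifies the threshold as the price of a timely answer. All of that stands. The 90% level is also a minimum reached only at study end, so most person-time is more complete than that.

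Several stronger readings are tempting but not supported:

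- A reader might infer that the bound is miscalculated because 10% and 11% appear in one paragraph. The 10% sentence says what is likely, and the maximum is correctly printed as 11%. No design quantity depends on the difference.
- A reader might treat the delay curve as known and the bias as fully removable. Section 5.2 only assumes that historical delays are accurately estimated, and a correction works only if they hold for this season.
- A reader might put the full 11% into the test and obtain rejection rates of 85% with 5,000 cases or 99% with 10,000. Those rates require the ceiling as the net bias and case counts that the protocol does not give. Analyses are by brand and outcome after substantial exclusions, so counts may be much lower.

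A delay adjustment might also sit in a statistical analysis plan that is not at hand. That answers a charge of omission. It does not remove the value of the suggestion: this protocol writes out the model, its offset and its sensitivity analyses, and argues for tolerating the bias. If the analysis plan already contains the adjustment, a cross-reference is enough.

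**Conclusion.** As written, the plan leaves an upward claims-delay bias in the primary IRR, and neither the primary model nor a planned sensitivity analysis addresses it. The bias is correctly bounded at 11%. Under the assumed uptake, cutoffs and delay shapes, the net figure for days 1-21 is roughly 0.5% to 8%, with the high end only for early cutoffs.

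Whether this matters depends on case numbers, which the protocol does not state. With about 1,000 cases and a 3% bias the false-positive rate barely moves. With about 5,000 cases and 3% to 5% it rises to between two and six times the nominal 5%. With a late cutoff and a bias below 1%, the effect is negligible even at 5,000 cases. It would therefore go too far to say outright that the nominal error rate fails.

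This is a cheap improvement. The difference between 10% and 11% is a matter of wording only.

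**What to change.** 1. Pre-specify an SCCS analysis, at minimum as a sensitivity analysis reported beside the primary one, in which log(t) is replaced by log(Σ ĉ(day)). The sum runs over the days of the interval, and ĉ is the estimated completeness on that calendar day at the data cut, by care setting and outcome. Take ĉ from the historical delay estimates already relied on to set the 90% cutoff.
2. State that a small but statistically significant IRR will be interpreted in light of this analysis.
3. In Section 5.2, align the 10% sentence with the maximum of about 11%.

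Cost: one changed offset and one further set of estimates, with no delay to the analysis. The main downside is dependence on the historical delay curve. If claims arrive faster or more slowly this season, the correction will over- or under-shoot, which is a reason to show both results.
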